### **Study design**

PROGRES 2.0 is a retrospective, multi-country, non-interventional, observational cohort study conducted voluntarily by Pfizer to assess the long-term effectiveness and safety of both a daily hGH Genotropin (somatropin) and a long-acting hGH Ngenla (somatrogon), at the discretion of the treating physician according to routine clinical care in a real-world setting. This study will gather the data as a sub-study of the Global Registry for Novel Therapies in Rare Bone and Endocrine Conditions (GloBE-Reg). Patient treatment with a particular therapy will be determined at the discretion of the treating physician according to routine clinical care.

The study is designed for strong generalizability and external validity. Its large sample size will allow the evaluation of key endpoints across various subgroups, while longitudinal data will assess the effectiveness and safety of Ngenla (somatrogon) and Genotropin (somatropin). Participants will be stratified by age, sex, puberty status, follow-up time, medical comorbidities, initial disease/treatment indications, peak GH levels, diagnosis, and region (Europe, Japan, North America, RoW/country). All assessments are part of normal clinical practice or standard guidelines in the countries where this non-interventional study is conducted.

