## 8. RESEARCH METHODS

### 8.1. Study Design

This is a multi-country, non-interventional, observational cohort study to assess the long-term effectiveness and safety of both a daily hGH Genotropin (somatropin) and a long-acting hGH Ngenla (somatrogon), at the discretion of the treating physician according to routine clinical care in a real-world setting.

The study will obtain data collected by the GloBE-Reg registry via a minimum data set, which was developed by an expert working group for monitoring the effectiveness and safety of both daily and long-acting GH in childhood GHD.

This study will have a broad geographic reach, including and participating centers are typically underrepresented in global studies. This will enable the evaluation of key primary and secondary endpoints, including the primary outcomes of interest: height, IGF-I, BMI, and bone age and secondary outcomes of interest: injection site reactions, immunogenicity and adherence. The longitudinal nature of the data will allow the evaluation of effectiveness and safety of Ngenla (somatrogon) and Genotropin (somatropin) and the endpoints will be evaluated within numerous prespecified strata or subgroups.

To evaluate the effectiveness and safety of Ngenla and Genotropin within the study population, participants will be stratified by select *a priori* subgroups, including but not limited to: age, sex, puberty status, follow-up time, medical comorbidities, initial disease/treatment indications, peak GH levels, diagnosis for GH disorder, and study region (Europe, Japan, North America, and Rest of the World [RoW]/country).

Strengths of this study design include the strong generalizability and external validity due to the large sample size from an international cohort of participants and the real-world clinical data that will be obtained.

All assessments described in this protocol are performed as part of normal clinical practice or standard practice guidelines for the participant's population and healthcare provider specialty in the countries where this non-interventional study is being conducted.

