## 8.7 Data Analysis

Data on the subset of participants in the GloBE-Reg registry who are treated with Ngenla (somatrogon) or Genotropin (somatropin) will be obtained and analyzed. The data will be converted to SAS format for analysis and reporting and will be processed by Pfizer to create analytical variables and datasets for all analysis specified in the study protocol. All study data will exist as structured data by the start of the study. Data obtained from GloBE-Reg will not undergo any additional cleaning or error checks, and there will be no imputation of missing data. All data received from GloBE-Reg will be analyzed. The study is descriptive in nature without *a priori* hypothesis testing.

090177e1a57a0182\Approved\Approved On: 16-Feb-2026 13:43 (GMT)

Analysis of Primary Endpoint:

The primary analysis is to compare effectiveness of Ngenla (Somatrogon) and Genotropin (Somatropin) during the course of routine clinical care. The primary endpoints are height, bone age, body mass index (BMI) and insulin-like-growth factor-I (IGF-I) levels.

The primary effectiveness outcomes for height (Annual HV, HVSDS, change in height SDS) will also be presented by subgroups. The following subgroups will be defined, as categorized at baseline.

- Age group (0 to 2, 3 to 8, 9 to 18, ≥19 years)
- Sex (Male, Female)
- Naïve/Non-naïve to rhGH therapy.
- Puberty Status (Yes, No)
- Medical co-morbidities (Yes, No)
- Initial disease/treatment indications (Yes, No)
- Peak growth hormone (GH) levels ≤3 ng/mL, >3 ng/mL to ≤7 ng/mL, >7 ng/mL to 10 ng/mL, > 10 ng/mL
- Primary Condition/Diagnosis (CKD, GHD (Non-specific, Acquired, Congenital, Idiopathic), Idiopathic Short Stature, Noonan Syndrome, Prader-Willi Syndrome, SGA, *etc.*)
- Study region (Europe, Japan, North America, Rest of the World)

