**Repeated Measures**

This model will only be performed with those patients without treatment switch until a given time point. Continuous variables will be analyzed by a Mixed Model for Repeated Measures (MMRM) under the MAR framework, including all post baseline timepoints data as outcome variables and baseline data as a covariate including the relevant patient/disease characteristics. Repeated time variable will be modeled as a continuous variable and treatment (Genotropin versus Ngenla) as a class variable with an unstructured covariance and least square means along with 95% CI will be presented.

The adjusted mean changes from Baseline at Month 6, 12, 18, 24, etc., for each treatment group will be estimated in the framework of this model, as well as the between group differences and the 95% CIs for the adjusted mean, when applicable.

The MMRM model will be implemented using SAS® (version 9.4 or higher) generalized linear mixed procedure (PROC MIXED) with an unstructured correlation matrix to model the within-patient errors. If this model does not converge, a heterogeneous Toeplitz covariance structure followed by the

090177e1a57a0182\Approved\Approved On: 16-Feb-2026 13:43 (GMT)

heterogeneous first-order autoregressive covariance structure will be considered. Parameters will be estimated using the Newton-Raphson algorithm. Denominator degrees of freedom will be estimated using the Kenward-Roger approximation.

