## 8.9 Limitations of the Research Methods

This is a non-interventional observational study, therefore, there are several potential limitations which are well-described in the literature for comparable studies, such as Kabi/Pfizer International Growth Database (KIGS) (13,14). As a retrospective cohort study, without randomization, there is a potential for variable quality and completeness of data. In addition, confounding and biases cannot be excluded, and determination of causation is limited. Enrollment or selection bias is possible since it is affected by the willingness or ability of physicians and patients to participate in GloBE-Reg. However, centers are expected to enroll all eligible patients treated with Ngenla (somatrogon) and Genotropin (somatropin). Follow-up bias is a potential limitation as well, especially if patients with AEs are less likely to return to the treating physician or center for follow-up.

Regarding the secondary endpoints on safety and adverse events, there is a potential risk of underestimating the safety outcomes due to underreporting, misreporting or missing data from the eCRFs, and/or EHR. The clinician entering data in the registry is responsible for evaluation of seriousness and causality of the safety and adverse events and due to the secondary collection of this data further investigation is limited.

Additional potential limitations specific to our study include:

- Data collection will reflect routine clinical practice rather than mandatory assessments at specified time points thereby increasing heterogeneity of the data. For this reason, visit windows (defined in the SAP) will be applied to the statistical analysis.
- The data source for this study is the subset of participants treated with either Ngenla (somatrogon) or Genotropin (somatropin) from the GloBE-Reg registry, which collects routine data from across the world and is reflective of different routine clinical practices according to region. This may lead to heterogeneity of the data and result in information bias. For this reason, subgroup analysis will be carried out for the primary efficacy

endpoints and pre-identified confounders will be included in the statistical models as presented in Table 9.3.

- Information bias may also occur related to risk of loss to follow up due to the long duration of this study or adverse event occurrence.

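### Participants are to be stratified by follow-up time, a post-baseline variable, in an open-ended a priori subgroup list that conflicts with the baseline list in Section 8.7

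*Protocol*

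**What the plan says.** Section 8.1 (Study Design) states that "participants will be stratified by select *a priori* subgroups, including but not limited to: age, sex, puberty status, follow-up time, medical comorbidities", and goes on to indication, peak GH, diagnosis and region. It adds that "the endpoints will be evaluated within numerous prespecified strata or subgroups", where the endpoints meant are both primary and secondary. The design summary in the Abstract names the same nine factors, follow-up time included, and says of the study: "Its large sample size will allow the evaluation of key endpoints across various subgroups".

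Section 8.7 (Data Analysis) restricts the scope to height: "The primary effectiveness outcomes for height (Annual HV, HVSDS, change in height SDS) will also be presented by subgroups". It then says "The following subgroups will be defined, as categorized at baseline" and lists nine factors, most with cut-points. Follow-up time is absent, naive/non-naive status is new, and the diagnosis factor ends with an open et cetera.

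Section 8.9 (Limitations) gives subgroup analysis a purpose, as one of two answers to heterogeneity between regional practices: "For this reason, subgroup analysis will be carried out for the primary efficacy" endpoints. The other answer is confounder adjustment in the models.

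Section 8.2 (Setting) ends a participant's follow-up at, among other events, discontinuation of either drug. The variables table in Section 8.3 records why therapy stopped; the options include poor efficacy, adverse events and attainment of final height.

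**The concern.** Two things are wrong on the face of the protocol.

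First, the sections do not agree on what the subgroups are. A list that can be added to later is not a priori, and one that is fixed at baseline cannot contain follow-up time. Scope also shifts, from all endpoints in Section 8.1 to three height outcomes in Section 8.7 and the primary efficacy endpoints in Section 8.9. A protocol amendment is promised only for major changes to primary endpoint definitions or their analyses, so an added subgroup need not trigger one.

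Second, follow-up time is not a characteristic that a participant brings to the study. If participants are grouped by how long they were followed, part of what places them in a group is how well they grew or tolerated treatment. A drug comparison within such a group is distorted however large the sample and however few subgroups are examined. The study makes comparison of the two drugs its primary aim, so such strata could feed directly into its conclusions.

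**Working it through.** **1. The lists side by side**

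| Factor | Abstract and Section 8.1 | Section 8.7 (levels) |
|---|---|---|
| Age | yes | 4 |
| Sex | yes | 2 |
| Naive/non-naive | no | 2 |
| Puberty status | yes | 2 |
| Comorbidities | yes | 2 |
| Indication | yes | 2 |
| Peak GH | yes | 4 |
| Diagnosis | yes | 9 named, then open |
| Region | yes | 4 |
| Follow-up time | yes | no |

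Each list has nine named factors, and they differ in one factor each way. Section 8.1 is open as a whole; Section 8.7 is open only within diagnosis. Section 8.7 has at least 4+2+2+2+2+2+4+9+4 = 31 levels.

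**2. Why realised follow-up is not a valid stratifier**

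- Follow-up ends at discontinuation (Section 8.2), and discontinuation can follow from poor growth, adverse events or completed growth (Section 8.3). Length of follow-up is therefore partly a result of the outcomes.
- Suppose one drug truly gives better growth. Those who stop early for poor efficacy are slow growers on either drug, so the short-follow-up group tends to understate the difference.
- Suppose growth is the same on both drugs but one is stopped more often for reasons unrelated to growth. The early stoppers on that drug then include more ordinary growers, and a difference appears where none exists.
- Late entrants also have short follow-up, for a purely administrative reason. A short-follow-up group mixes them with early stoppers.

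The protocol gives no stopping rates by drug or by growth response, so the size of this bias cannot be computed from it.

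**3. Context: chance findings over the Section 8.7 grid**

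The protocol states no error rate for subgroups, so there is no figure to reproduce. Inputs: 2000 and 700 expected participants (Section 8.5), 31 levels, three height outcomes, nominal 95% intervals. Assumed: no true drug difference, a between-drug interval reported in every level, and equal-sized levels from unrelated factors.

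If all intervals were independent:

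- One outcome, one time point: 1 − 0.95^31 = 0.796.
- Three outcomes, 31 × 3 = 93 intervals: 1 − 0.95^93 = 0.992.

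The same participants recur under every factor, so the intervals are not independent. A null simulation (600 replicates per setting) gives:

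| Setting | P(at least one interval excludes zero) |
|---|---|
| One outcome, one time point | 0.65–0.71 |
| Three outcomes, correlation 0 | 0.96 |
| Three outcomes, correlation 0.5 | 0.95 |
| Three outcomes, correlation 0.8 | 0.89 |
| Three outcomes, correlation 0.5, unequal level sizes | 0.97 |

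With one interaction test per factor on one outcome and time point instead, the chance of at least one false signal is 1 − 0.95^9 = 0.37 (simulated 0.35–0.40). Interaction tests reduce the problem but do not remove it, so the fix asks for interaction estimates with intervals rather than significance tests.

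**The case against.** The strongest reply is that Section 8.7 is the operative text for height. It names three outcomes and a baseline list without follow-up time, while Section 8.1 and the Abstract are general design prose. This stands. A reader might infer that the height comparison will be split by follow-up time in an open-ended set; Section 8.7 does not support that. The conflict still needs resolving, because Section 8.1 covers the endpoints generally and says outright that participants will be stratified by follow-up time.

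Follow-up time might also mean only time on study, as in the repeated-measures section: "The adjusted mean changes from Baseline at Month 6, 12, 18, 24, etc., for each treatment group will be estimated". That reading would be harmless. No section defines it, however, and both places list it among participant characteristics such as age and sex.

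A reader might also fault the lack of an interaction test or an exploratory label. The documents do not support that as a defect. Detailed methods are deferred to a SAP that is not at hand, and the study is declared descriptive with no hypothesis tests. That declaration sits uneasily with a comparative primary aim, but it does cover the subgroup results.

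Finally, Section 8.7 says that outcomes are presented by subgroup, not that a drug difference is computed in each. The repeated-measures section plans "as well as the between group differences and the 95% CIs for the adjusted mean, when applicable" without mentioning subgroups. Reading within-level differences into the plan is reasonable but remains an inference, and every figure in part 3 of the working depends on it.

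**Conclusion.** The point holds as a contradiction between sections plus one unsuitable stratifier. The Abstract and Section 8.1 cannot stand beside Section 8.7, and a drug comparison within groups formed by realised follow-up would be biased unless stopping is unrelated to growth and tolerability, which the protocol's own stop reasons contradict. The direction and size of that bias cannot be fixed from the document.

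The multiplicity figures are supporting context, under the assumptions listed with them: about 65–71% for one height outcome at one time point and 89–96% for three. It is tempting to say that a chance subgroup difference is close to certain. That holds only if the full grid of about 93 intervals is scanned as if each were a test, in a study that plans none. Nor do the documents require withdrawing the Abstract's sentence on sample size and subgroups, or forbidding any statement about a single level; those would be preferences.

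**What to change.** - Make the baseline list in Section 8.7 the single list in the Abstract, Section 8.1 and Section 8.7. Delete the words in Section 8.1 that leave the list open, and replace the et cetera in the diagnosis factor with named categories.
- Remove follow-up time as a way of grouping participants. Report effectiveness by analysis month, as the repeated-measures section already does, and safety by interval of time on treatment.
- Where drug differences are shown by subgroup, label them exploratory and give the treatment-by-subgroup estimate with its 95% CI.

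The cost is wording in three places and one interaction term per subgroup model. The downside is that weaker subgroup statements will be permitted.

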### 8.2. Setting

The source population for this study will be the subset of patients contributing data to the GloBE-Reg registry who are treated with either long acting Ngenla (somatrogon) or daily hGH Genotropin (somatropin) at the discretion of the prescribing physician. This population is thought to be a representative sample of children treated with Ngenla (somatrogon) and Genotropin (somatropin) across the world. Data will be included from eligible participants of any age who meet the study criteria and who receive care at centers enrolled in GloBE-Reg that have agreed to share their data with Pfizer during the data collection period. The registry is growing and additional centers around the world are expected to be included over the course of the study period.

The data collection period is from September 30, 2025 to August 31, 2035. No sampling will be performed. Participants can be located anywhere in the world and will be followed up to 10 years until the end of the study or one of the following occurs: withdrawal of consent, discontinuation of

either Ngenla (somatrogon) or Genotropin (somatropin), discontinuation from the GloBE-Reg registry, lost to follow up or death.

The treating physician will follow patients treated with Genotropin (somatropin) or Ngenla (somatrogon) as per routine clinical practice and will collect and enter relevant patient data as part of the defined minimum data set collected by the GloBE-Reg registry.

During the study, duration of treatment exposed will be defined as:

Genotropin/Ngenla: (last dose date – baseline date + 1)/365.25,

where baseline date is the initial visit date on the Reported Outcomes eCRF form.

The data collected via GloBE-Reg will be de-identified and sent to Pfizer for analysis. Pfizer will analyze the data to evaluate treatment effectiveness, safety, adherence and compliance.

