
Country(ies) of study
	
Armenia, Belgium, Brazil, Bulgaria, China, Czech Republic, France, Georgia, Germany, Hong Kong, Italy, Malaysia, Poland, Portugal, Saudi Arabia, Slovenia, Sri Lanka, United Kingdom, United States
 
Additional countries will be included as the GloBE-Reg registry expands.

Author
	

090177e1a57a0182\Approved\Approved On: 16-Feb-2026 13:43 (GMT)

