#### Rationale and background

Human growth hormone (hGH) is a 191-amino-acid pituitary protein that stimulates production and release of insulin-like growth factor-I (IGF-I). Growth hormone (GH) and IGF-I are the primary mediators of the promotion of growth in children and play a role in the regulation of body composition and metabolism in children and adults. Growth hormone deficiency (GHD) results in inadequate levels of GH and IGF-I, which subsequently results in abnormal linear growth in children. Children with GHD have been treated with daily administration of recombinant hGH replacement therapy for many years which has been proven to be safe and effective.

Recombinant hGH has also been approved in many countries around the world for other conditions associated with growth failure and/or abnormal body composition. Children with GHD, Turner Syndrome (TS), Small for Gestational Age (SGA) and Idiopathic Short Stature (ISS) have been treated with daily administration of recombinant hGH replacement therapy for many years. Children with Prader-Willi syndrome (PWS) have also been treated with hGH for both the associated growth failure and abnormal body composition.

The burden of daily administration may cause sub-optimal adherence and limit the therapeutic utility of existing formulations of recombinant hGH. Ngenla (somatrogon) is a long-acting, once-weekly subcutaneously administered form of hGH, currently approved in many countries around the world for use as a long-term treatment in children with growth failure due to an inadequate secretion of endogenous GH.

PROGRES 2.0 is a multi-country, non-interventional, observational cohort study with the objective to assess the long-term effectiveness and safety of both Genotropin (somatropin) and Ngenla (somatrogon), at the discretion of the treating physician in routine clinical practice. This study will obtain real world data as a sub-study of the Global Registry for Novel Therapies in Rare Bone and Endocrine Conditions (GloBE-Reg). GloBE-Reg is an international registry project that obtains data on effectiveness and long-term safety through the collection of real-world data on all available forms of growth hormone and supports sub-studies focusing on various aspects of interest to treating

090177e1a57a0182\Approved\Approved On: 16-Feb-2026 13:43 (GMT)

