### 8.2.1. Inclusion Criteria

Participants must meet all the following inclusion criteria to be eligible for inclusion in the study:

1. Receiving treatment with either Ngenla (somatrogon), or Genotropin (somatropin), at the discretion of the prescribing physician.
2. Confirmation of consent to participate in the GloBE-Reg registry and consent to have data shared with Pfizer as part of the PROGRES 2.0 sub-study.

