**Table 8-3 Model Covariates**

Priority Order*	Model Covariates	Propensity Score Model Covariates - Categories
7	Geographic region	Region (Europe, NA, Japan and RoW)
1	Demographics	Age (in years), Sex
2	Clinical characteristics	Height, Weight
3	Naive to GH status	Naïve to GH/Non-Naïve to GH
4	Peak GH levels	≤3 ng/mL, >3 ng/mL to ≤7 ng/mL, >7 ng/mL to 10 ng/mL, >10 ng/mL
5	Duration of GH (time from first rhGH therapy)	
6	Time since start of the study (in months)	

090177e1a57a0182\Approved\Approved On: 16-Feb-2026 13:43 (GMT)

\*This priority order will be used to remove the least priority variables in case of non-convergence issues for the model. Additional variables and its priority order can be decided during the analysis. Relevant patient/disease characteristics, including baseline value of the variable to be analyzed, will also be included whenever applicable.

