## 8.6. Data Management

All data for this study will be collected through the routine data collection practices of the GloBE-Reg registry. Investigators in each country will independently generate the data needed for the registry. The investigators will check the data for consistency in terms of range of values, units of measurement, and relevance of clinical information.

The registry is a web-based interface linked to a secure database at the University of Glasgow, and investigators at centers around the world add pseudonymized, routinely collected clinical data on patients who provide consent to participate in the registry. Data contained in other databases and registries can also be uploaded using a bulk transfer method, which avoids manual double entry through bulk upload of core and longitudinal data.

All participant data is stored by GloBE-Reg on a secure physical server at the University of Glasgow, which is managed and reviewed by Central IT Services. Additional details can be found in University of Glasgow's Data Protection Impact Assessment (DPIA) document (Annex 1).

Data for participants treated with Ngenla (somatrogon) and Genotropin (somatropin) will be provided to Pfizer only after centers provide consent to share their data. Data transferred to Pfizer will be in CSV format every 6 months using CONFORM 4.0.10 or later via secure file transfer protocol and stored internally on a secured dedicated server. The data will be converted to SAS format for analysis and reporting and will be processed by Pfizer to create analytical variables and datasets for all analyses specified in the study protocol. All study data will exist as structured data by the start of the study. The data analysis and results generation will strictly follow the approved SAP. If for any reason any statistical method needs to be carried out differently than described in the SAP, an amendment to the SAP with required documentation and new approval will be done. All computations and generation of Tables, Listings and Data for figures will be performed using SAS Version 9.4 or higher.

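### The between-drug comparison does not require that Ngenla was in use in the Genotropin patients' country and period, and its only geographic adjustment is a coarse region term that is the first to be dropped

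*Protocol*

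**What the plan says.** Protocol 8.7 makes the comparison of the two products the primary analysis. Its repeated-measures text plans adjusted between-group differences with 95% CIs.

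Eligibility rests on exposure and consent. The first criterion in 8.2.1 is "Receiving treatment with either Ngenla (somatrogon), or Genotropin (somatropin), at the discretion of the prescribing physician". The second is consent to the registry and to data sharing. Section 8.2.2 excludes only interventional-trial participants and data that fail the registry's quality checks. On geography, 8.2 says "No sampling will be performed. Participants can be located anywhere in the world".

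On time, 8.2 says "The data collection period is from September 30, 2025 to August 31, 2035". Exposure is counted from baseline, "where baseline date is the initial visit date on the Reported Outcomes eCRF form". No earliest baseline date is given. Section 8.6 adds "Data contained in other databases and registries can also be uploaded using a bulk transfer method".

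On Ngenla's availability the abstract says only that it is "currently approved in many countries around the world for use as a long-term treatment in children". It gives no country list and no launch dates.

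The one geographic covariate in Table 8-3 is "Region (Europe, NA, Japan and RoW". It carries priority number 7, the last, and time since study start carries 6. The table's footnote says the lowest-priority variables are removed when a model does not converge. The title pages list 19 countries, beginning "Armenia, Belgium, Brazil, Bulgaria, China, Czech Republic, France, Georgia, Germany, Hong Kong", and say that more will be added.

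**The concern.** A comparison of two products chosen at the physician's discretion is easiest to interpret where either could have been chosen. A Genotropin patient treated where Ngenla is not in use had no chance of receiving it. If such patients enter the control group, whatever is different about their countries (diagnostic habits, dosing practice, access) falls on the Genotropin side only. The model then needs a covariate fine enough to separate country from drug. Section 8.9 acknowledges that routine practice varies by region and relies on subgroup analyses and the tabled confounders to deal with it. The geographic confounder in that table is both coarse and the most expendable.

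What is at stake is the reading of the adjusted difference and its CI, for the MMRM, the MMRM with IPTW, the incidence rate ratio and the hazard ratio alike.

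**Working it through.** The protocol derives no figure on this point. Section 8.5 states 2000 Genotropin and 700 Ngenla patients as an expectation, so there is no calculation to reproduce.

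**1. How coarse is region?** The 19 listed countries split as follows:
- Europe, 10: Belgium, Bulgaria, Czech Republic, France, Germany, Italy, Poland, Portugal, Slovenia, United Kingdom.
- North America, 1: United States.
- Japan, 0.
- Rest of the world, at least 6: Brazil, China, Hong Kong, Malaysia, Saudi Arabia, Sri Lanka.
- Armenia and Georgia, 2, depending on classification.

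So 18 of the 19 countries fall into two levels. Section 8.3 collects site ID and country of residence, but neither is in Table 8-3.

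**2. Form of the bias.** Within a region, let m be the Genotropin mean where Ngenla is in use and δ the true drug effect. Let p be the share of Genotropin patients in settings without Ngenla, and d their residual difference after the other covariates.

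- Genotropin mean = (1 − p)·m + p·(m + d) = m + p·d
- Ngenla mean = m + δ
- Contrast = δ − p·d, so the bias has size p × |d|

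Weighting does not remove it. A propensity model that sees only region gives these patients the same fitted probability of Ngenla as otherwise similar patients in their region, although their true probability is zero.

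**3. Illustration only.** p and d are assumed, because the protocol gives neither. Bias in annual height velocity, cm/year:

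| p | \|d\| = 0.5 | \|d\| = 1.0 | \|d\| = 1.5 |
|---|---|---|---|
| 0 | 0 | 0 | 0 |
| 0.1 | 0.05 | 0.10 | 0.15 |
| 0.2 | 0.10 | 0.20 | 0.30 |
| 0.3 | 0.15 | 0.30 | 0.45 |

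For scale, the expected precision is SE = SD × √(1/2000 + 1/700). With an assumed SD of 2, 2.5 or 3 cm/year this gives 0.088, 0.110 or 0.132, and 95% CI half-widths of 0.17, 0.22 or 0.26.

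**4. Simulation check.** Settings: 2000 versus 700 patients, SD 2.5, true drug effect 0, assumed region shares of 60/5/35%, linear model with drug and region at one time point, 400 replicates.

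| p | d | Bias, region-adjusted | 95% CI coverage |
|---|---|---|---|
| 0.1 | −0.5 | +0.05 | 93% |
| 0.1 | −1.0 | +0.10 | 86% |
| 0.2 | −0.5 | +0.10 | 85% |
| 0.2 | −1.0 | +0.20 | 54% |
| 0.4 | −0.5 | +0.20 | 57% |
| 0.4 | −1.0 | +0.41 | 5% |

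Restricting Genotropin patients to settings with Ngenla leaves bias of at most 0.01 and coverage of 94–96% in every case.

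**5. Cost of restriction.** If half the Genotropin patients are excluded: √(1/1000 + 1/700) ÷ √(1/2000 + 1/700) = 0.0493 ÷ 0.0439 = 1.12. At SD 2.5 the half-width goes from 0.215 to 0.241 cm/year.

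**The case against.** Several points on the other side are sound.

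- **Period.** A reader might infer a control group reaching back over decades of Genotropin use. The documents do not support that. Collection runs from 2025 to 2035. Annex 3 says that the registry launched in 2022 and that data cannot be entered without consent, and 8.4 applies the same requirements to bulk upload. What remains is that no lower limit is set on the baseline date. The registry already held 365 Genotropin and 157 Ngenla patients on 30 June 2025, before collection opened.
- **Availability.** A reader might take it as established that some listed countries have no Ngenla. The protocol names none. The possibility is inferred from the wording on approvals and from the open country list.
- **Japan.** The Japan level matches no listed country, but an empty level drops out of the model without harm and may fill later.
- **Other covariates.** Age, sex, height, weight, prior GH exposure, peak GH and GH duration are also in Table 8-3 and would absorb part of any country difference. Only the residual d counts. Dosing practice and access have no counterpart in the table.
- **Flexibility.** Country appears beside the rest of the world in the stratification text of 8.1, and the Table 8-3 footnote lets variables be added. But the subgroup list in 8.7 uses region only, and a covariate chosen during the analysis is not prespecified.
- **Scope.** Section 8.7 calls the weighted model a sensitivity analysis for switching, 8.9 concedes that confounding cannot be excluded, and overlap diagnostics belong in the SAP. That is fair. Eligibility, the covariate list and the drop order, however, are set in the protocol.

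**Conclusion.** The point stands as a weakness in how the comparison is specified. Eligibility does not tie Genotropin patients to countries and periods in which Ngenla was in use. The geographic adjustment cannot separate countries within Europe or the rest of the world. The two covariates closest to availability, region and time since study start, are the first and second to go on non-convergence.

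The documents do not show that the result will be biased, or by how much. The bias is about p × d and vanishes if either is zero. A reader might set the illustrative values against the Phase III difference in section 6 (10.10 − 9.78 = 0.32 cm/year) and quote a percentage. That would multiply two assumed inputs and divide by a figure that is neither a margin nor a target here. The working shows only that moderate values, such as p = 0.2 with |d| = 1.0, would give a bias close to the expected CI half-width. It rests on an assumed SD and a simplified single-time-point model without the other covariates.

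The change is worth making because it is specific and inexpensive and draws mainly on fields already collected.

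**What to change.** 1. In Table 8-3, replace region with country or centre, either as a random effect or with small countries pooled by a rule stated in advance. State that this term and calendar time are not removed on non-convergence.
2. Prespecify a between-drug analysis (MMRM, MMRM with IPTW, incidence rate ratio, hazard ratio) restricted to countries and calendar periods in which both products are in use. Report it beside the unrestricted comparison.
3. Define the start of each such period by the local availability date. The first Ngenla record in the registry should not be the only criterion, because it also depends on when centres joined and entered data.
4. Keep all patients in the descriptive tables.

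**Cost.** Protocol and SAP wording, a filter on collected fields (site, country, visit date, product) and a list of local availability dates. CIs become wider: about 12% if half of the 2000 Genotropin patients are excluded, and somewhat more once country terms are added, particularly where countries are small or dominated by one product. The 12% is therefore not an upper bound.
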